### 10.8.2. Suspension of Study Drug Administration

Study drug administration will be suspended temporarily in subjects with a case of suspected sepsis (see [Section 10.3.5.1](#)) or infection of a normally sterile site (see [Section 10.3.5.2](#)). Study drug may be re-initiated at the discretion of the Investigator, if the subject's clinical condition permits and:

- Cultures are negative for gram positive bacilli or,

- STP-206 organisms are not confirmed by central laboratory analysis.

Additionally, dosing of blinded study treatment may be withheld at the discretion of the physician Investigator. The reason for suspension of blinded study treatment will be documented in the subject's source documents and the case report form.

Neonates will be discontinued from the study if:

- Dosing is suspended for greater than seven consecutive days or
- More than two suspensions of oral dosing of five or more consecutive days each in duration are required.

If the neonate is placed on NPO status for suspected NEC and the NPO status is maintained for greater than 24 hours, dosing of blinded study drug will be suspended until NPO status is removed.

If NEC is diagnosed, study drug administration will be immediately discontinued.

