#### 12.2.4. Relationship to Study Drug

The Investigator must attempt to determine if an AE is in some way related to the use of the study drug. This relationship should be described based upon the following definitions:

- **Unrelated/Not Related:** The AE is clearly due to causes distinct from the use of the study drug, such as a documented pre-existing condition, the subject’s clinical state, environmental factors, the effect of other concomitant medications or treatments administered.
- **Unlikely:** The AE does not follow a reasonable temporal sequence from administration of the study drug, does not follow a known response pattern to the study drug, and could readily have been due to other causes such as the subject’s clinical state, environmental factors, the effect of other concomitant medications or treatments administered.
- **Possible:** The AE follows a reasonable temporal sequence from administration of the study drug and follows a known response pattern to the study drug, *BUT*, the AE could readily have been produced by the subject’s clinical state, environmental factors, the effect of other concomitant medications or treatments administered.
- **Probable:** The AE follows a reasonable temporal sequence from administration of the study drug and follows a known response pattern to the study drug *AND* cannot be reasonably explained by the subject’s clinical state, environmental factors, the effect of other concomitant medications or treatments administered. The event improves upon discontinuation of the study drug.
- **Definite/Related:** The AE follows a reasonable temporal sequence from administration of the study drug and follows a known response pattern to the study drug. Based on the known pharmacology of the study drug, the event is clearly related to the effect of the study drug. The AE improves upon discontinuation of the study drug and reappears upon repeat exposure.

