### 13.2.3. Data Analysis

Details regarding the data analyses planned for the study will be outlined in the statistical analysis plan (SAP). Any changes to planned methods and analyses will be described and justified in the SAP, as appropriate. The SAP will be finalized prior to database lock.

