#### *13.2.3.2. Safety Data Analysis*

AEs will be assessed from the time the subject receives the initial dose of study drug through 6 months following the last dose. AEs will be coded according to Medical Dictionary for Regulatory Activities (MedDRA) and summarized in frequency tables displaying counts and percentages by body system, preferred term, and treatment group. Subjects reporting multiple events will only be counted once.

In addition, AEs will be summarized by relationship to study drug and by severity. For assessing relationship to study drug, any event with a study drug relationship marked as “possible”, “probable” or “definite/related” on the CRF will be considered related to study drug.

All SAEs will also be summarized in a frequency table.

Medical history (maternal, pregnancy and infant), concomitant medications, and physical examination findings, will also be summarized by treatment group at each timepoint where data was collected.

Information on method (bottle, breast, tube) and content of feedings (formula or breast milk) will be summarized.

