#### 13.2.5. Reporting of Deviations to Statistical Methodology

Any deviations to the protocol defined analysis will be documented in the SAP. Deviations in analyses described in the SAP will be documented in the study report.

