5.2 Changes from the Analyses Planned in the Protocol

The definition of the Intent-to-treat analysis population was changed in this SAP to include all subjects that are randomized regardless of dosing status.

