8.7 Analysis of Safety

Safety population will be used for the analysis of Safety.

Safety data will be displayed by (i) dose group and BW stratum and (ii) by all BW strata combined for STP206 low dose, STP206 high dose and control group.

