8.7.2 Adverse Events

All AE summaries will be presented by the safety population.

All AE tables will include only treatment emergent AEs (TEAEs) unless otherwise noted. TEAEs are those which start or worsen in severity after the first dose of study medication. If it

cannot be determined if the AE started or worsened after the first dose of study treatment, it will be assumed to be a TEAE.

AEs will be assessed from the time the subject receives their initial dose of study medication up to 6 months following the last dose of study drug (note that some sites used 6 months gestational age rather than 6 months post last dose). All AEs reported during this period, regardless of severity relationship to blinded study treatment, will be recorded. The investigator's verbatim term of each adverse event will be mapped to the system organ class and preferred term using the MedDRA dictionary.

All AE tables will be summarized for each treatment group by system organ class (SOC) and preferred term (PT) using counts and percentages.

In order to count the number of subjects who experienced each AE, a subject experiencing the same AE multiple times will only be counted once for the corresponding preferred term. Similarly, if a subject experienced multiple AEs within the same SOC, that subject will be counted only once for that SOC. Adverse events will be presented in alphabetical order of SOC and within each SOC, in decreasing order of the total number of subjects who experienced each AE at the preferred term level.

Adverse events will also be presented by severity for Mild AE (Grade 1), Moderate AE (Grade 2) and Severe AE (Grade 3). In the case of multiple experiences with the same AE, the subject will be counted only once under the worst reported severity. Missing category will be presented to summarize any missing severity.

Serious adverse events (SAEs) will be presented by SOC and preferred term.

Adverse events will also be summarized by relationship. Treatment related AEs include those events that were rated by the investigator as possible or probable related. Missing category will be presented to summarize any missing relationship.

The following AE categories will be summarized:

- Overall AE summary
- AEs by SOC and preferred term
- Related AEs by SOC and preferred term
- Grade 3 AEs by SOC, preferred term and relationship to study treatment
- Treatment Related AEs with Grade 3 by SOC, preferred term

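### The SAP's definition of a treatment-related adverse event leaves out the protocol's strongest causality rating, definite/related, and does not declare the change

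*SAP*

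**What the plan says.** Protocol 12.2.4 sets up a five-level causality scale: unrelated, unlikely, possible, probable and definite/related. The top level has the most demanding conditions, among them that "The AE improves upon discontinuation of the study drug and reappears upon repeat exposure".

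Protocol 13.2.3.2 then gives the analysis rule: "any event with a study drug relationship marked as “possible”, “probable” or “definite/related” on the CRF will be considered related to study drug".

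SAP 8.7.2 gives a different rule: "Treatment related AEs include those events that were rated by the investigator as possible or probable related". The SAP has no other definition of a treatment-related event.

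On changes, Protocol 13.2.3 states: "Any changes to planned methods and analyses will be described and justified in the SAP, as appropriate". Protocol 13.2.5 adds: "Any deviations to the protocol defined analysis will be documented in the SAP". SAP 5.2 records one change only: "The definition of the Intent-to-treat analysis population was changed in this SAP to include all subjects that are randomized regardless of dosing status". SAP 5.1 and 5.3 say nothing about AE causality.

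**The concern.** The two documents give different rules for the same set of tables, and the SAP's rule makes no sense as a deliberate choice: it keeps the weaker ratings and leaves out the strongest. A programmer working from SAP 8.7.2 would select possible and probable, and would drop any event the investigator had judged clearly attributable to study drug.

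Safety and tolerability is the primary objective. Related-AE tables that omit the most strongly attributed events are hard to defend to a regulator or to anyone deciding on further development. Compared with the protocol rule, the SAP rule can only lower related-AE rates. Because study treatment is blinded, a definite/related rating could be given in either arm, so the direction of any effect on the comparison with control is not fixed.

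**Working it through.** **Comparison of the two rules**

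| Causality rating (Protocol 12.2.4) | Related under Protocol 13.2.3.2 | Related under SAP 8.7.2 |
|---|---|---|
| Unrelated/not related | No | No |
| Unlikely | No | No |
| Possible | Yes | Yes |
| Probable | Yes | Yes |
| Definite/related | Yes | Not named |

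The rules differ in one category, definite/related.

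**Outputs affected (SAP section 11)**

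- Related TEAEs, Tables 14.3.1.5.1-3: the event is missing.
- Grade 3 related TEAEs, Tables 14.3.1.6.1-3: the event is missing if it is Grade 3.
- Overall TEAE tables, 14.3.1.2.x: the event is missing from any related count they contain.
- All-TEAE tables, the SAE, discontinuation and death tables where they apply, and the AE listings: unaffected.

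**Can the category occur?** Yes. It needs recurrence on re-exposure, and dosing can be interrupted and resumed. Protocol 10.8.2 says that "dosing of blinded study treatment may be withheld at the discretion of the physician Investigator". The same section allows study drug to restart after suspected sepsis or a sterile-site infection, and it limits the length and number of suspensions, which implies that dosing can resume. The documents do not say how often the rating was used.

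**Size of the effect per infant.** The documents give no affected count, so the only available measure is the weight of one infant who has a definite/related event and no other related event.

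- Planned cohort (Protocol 7.1): 12 infants randomized 2:1, so 12 × 2/3 = 8 on STP206 and 12 × 1/3 = 4 on control.
- Pooled display (SAP 8.7): "by all BW strata combined for STP206 low dose, STP206 high dose and control group". Each dose group has 4 strata × 8 = 32 infants, and control has 8 cohorts × 4 = 32. The total is 32 + 32 + 32 = 96.
- Cohort STP206 arm: 1/8 = 12.5 points.
- Cohort control arm, if shown separately for each cohort: 1/4 = 25 points. If the two control sets in a stratum are combined, 1/(4 + 4) = 12.5 points.
- Pooled dose group or pooled control: 1/32 = 3.1 points.
- At the upper enrollment figure of 110 (Protocol 9.1), assuming an even split between doses: 110 × 2/3 ÷ 2 = 36.7 per dose group, and 1/36.7 = 2.7 points.

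**The case against.** The best defense is that the SAP says related events include the two named ratings, not that they are limited to them. Since leaving out the strongest rating has no rationale, this reads as a drafting omission, in which case there was no intended change to declare. The table shells are a separate document and may treat the category correctly. That is all possible. But no text in the SAP restores the category, and a sentence naming two of the protocol's three ratings is what a programmer is likely to code.

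The second point is that SAP 8.7.2 also promises summaries by relationship, including one for Grade 3 events, which could show definite/related events. However, none of the AE table titles in SAP section 11 refers to individual causality categories, so this cannot be confirmed. Even if such a table is produced, it would not correct the related-AE tables.

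The third point stands in full: the practical effect may be small or nil. The primary endpoint concerns the incidence and severity of AEs and SAEs and has no relatedness filter. The unfiltered outputs are intact, statistical comparisons are exploratory only, and the stopping criteria work through DSMC review of individual events. The conditions for a definite/related rating are demanding, so there may be no such event. This limits the likely damage but does not justify an analysis rule that is right only if one CRF category stays empty.

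**Conclusion.** The concern holds. SAP 8.7.2 contradicts Protocol 13.2.3.2 on which events count as related, and the difference is not declared where the protocol says it should be. Followed literally, the SAP can only understate related-AE rates.

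The mismatch in wording is certain, but its numerical effect is not. The per-infant figures assume cohorts filled as planned at 12 with an exact 2:1 split, and an infant with no possible or probable event that would keep it in the count. They show what one omission would do and do not predict that any will occur. The primary endpoint and the unfiltered safety outputs are not altered. The point is worth correcting because it affects named safety tables in a safety trial and the correction is trivial.

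**What to change.** Reword the sentence in SAP 8.7.2 so that treatment-related AEs are those the investigator rated possible, probable or definite/related, in line with Protocol 13.2.3.2. Apply the same condition to every related-AE output: Tables 14.3.1.2.x, 14.3.1.5.x and 14.3.1.6.x. Check the separate table shells for the same omission.

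If the narrower rule was in fact intended, it should be declared and justified in SAP 5.2, although the documents offer no reason for it.

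The cost is one SAP sentence and one programming condition. No additional data are needed, because the protocol's rule already refers to this rating on the CRF.

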8.7.3 Clinical Laboratory Evaluations

Blood cultures will be collected upon NICU admission (if SOC medium for the study site), and during the dosing period when sepsis is suspected. Data from blood cultures will be provided in a listing.

Site cultures will be collected if an infection of a normally sterile site (e.g., UTI, peritonitis) is suspected. Data from site cultures will be provided in a listing.

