#### **6.3.2. Secondary Endpoints**

The secondary endpoints of the study are:

- The incidence and the severity of AEs and SAEs in STP206-treated subjects compared to control subjects from baseline through six months after the last dose of blinded study treatment
- The incidence of clinical events (NEC, sepsis/bacteremia, feeding intolerance, death, morbidity/complications of prematurity) in STP206-treated subjects compared to control subjects from baseline through hospital discharge
- The assessment of the fecal shedding of STP206 organisms in STP206-treated subjects compared to its baseline and to control subjects through the last dose of blinded study treatment

- The assessment of the changes in routine clinical parameters in STP206-treated subjects compared to control subjects at baseline through the last dose of blinded study treatment
- The assessment of the progression of standard neonatal growth parameters in STP206-treated subjects compared to control subjects through the 6-month postdosing visit.

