### 7.1.1. Stopping Criteria

The following stopping events reported to Leadiant will be evaluated by the DSMC to assess whether the events merit a temporary suspension or stopping study enrollment:

- Any death due to an AE assessed to be directly related to the administration of STP206
- Isolation of an STP206 organism from a normally sterile site (including bacteremia but excluding peritonitis in association with intestinal necrosis) in any subject

All reports of stopping events will be forwarded to the DSMC for review. If either of the above events occurs, enrollment will be suspended temporarily while the DSMC is evaluating the event. Subjects on blinded study drug will continue dosing during the assessment of the event.

If a stopping criterion is met, the DSMC will perform an unblinded review of the event to assess causality and its overall impact on subject safety and provide its recommendations to Leadiant. If an event, in the opinion of the DSMC, is related to the administration of STP206, dosing of all ongoing study subjects will be halted, and the study will be suspended temporarily. FDA will be notified of all DSMC's recommendations before taking any actions with the study.

A flow diagram for the process of evaluating infections of normally sterile sites that are suspected to be associated with STP206 organisms (*i.e.*, gram positive bacilli) is provided in [Appendix E](#).

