### 10.3.5.1. Assessment and Treatment of Sepsis

The Investigator will initiate a work-up for suspected sepsis (including the involvement of either one of the two bacteria strains in STP206) for full evaluation, diagnosis, and treatment, if indicated by clinical signs and symptoms.

In the case of suspected sepsis, the Investigator will:

- Perform full clinical evaluation of the subject.
- Study drug treatment will be suspended temporarily. Study drug treatment may be re-initiated at the discretion of the Investigator based on the subject's clinical condition (see [Section 10.8.2](#)).
- Obtain peripheral blood cultures (*i.e.*, not through a central line) for aerobic and anaerobic pathogens to identify the offending pathogen(s) prior to initiating antibiotic treatment. If obtaining a culture prior to initiation of antibiotics is not possible, a culture should be collected as soon as possible following initiation of antibiotic treatment.
- If the site's local laboratory identifies gram positive bacilli in the blood culture, a sample of the isolate will be forwarded to the central laboratory for qPCR analysis to confirm, if the offending bacteria are ██████████ STP11 or ██████████ STP6.
- Start treatment with antibiotics, as appropriate.
- Clinical management, monitoring (*e.g.*, clinical signs, vital signs, X-rays, and laboratory investigations) and supportive care of the subject will be based upon the treatment protocol(s) of the institution and the discretion of the treating physician and/or Principal Investigator based upon the individual subject requirements and changes in clinical status over time.
- Feeding will be continued or adjusted based upon subject stability as determined by the treating physician and/or Principal Investigator (*e.g.*, stable neonates may continue to be on enteral feeds, while infants with respiratory distress or suspected NEC will receive nothing by mouth (NPO) and be maintained on intravenous fluids).
- If the initial cultures obtained were positive, obtain a repeat set of aerobic and anaerobic cultures to assess response to antibiotic treatment.

The Investigator will maintain and/or obtain medical records pertaining to the management, treatment, and outcome of the event for the purpose of AE/SAE reporting.

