8.6 Analysis of Efficacy Parameters

Descriptive summaries will consist of frequencies and percentages for categorical measures and of the number of subjects [N], mean, standard deviation [SD], median, 25th and 75th quartiles, minimum [min], and maximum [max] values for continuous measures. Descriptive summaries will be presented for each treatment group, BW strata, and all BW strata combined.

The incidence rates of the exploratory variables for those who received STP206 vs. control will be summarized and displayed.

The analyses of efficacy variables will be performed for ITT population only.

Efficacy will be displayed by (i) dose group and BW stratum and (ii) by all BW strata combined for STP206 low dose, STP206 high dose and control group.

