8.6.2 Analysis of Secondary Efficacy Variables

8.6.2.1 Endpoints

- Incidence of suspected NEC (Stage I)
- Incidence of confirmed NEC (Stage II and higher)
- Incidence of sepsis/bacteremia
- Incidence of feeding intolerance
- Hospital Mortality (death occurred during inpatient hospitalization)
- Incidence of other neonatal complications of prematurity
 - ROP
 - IVH
 - BDP
 - Spontaneous Gastrointestinal Perforation
 - Patent ductus arteriosus requiring treatment with indomethacin, ibuprofen or surgery

The incidence rate of each outcome will be summarized separately. The secondary efficacy will be displayed by (i) dose group and BW stratum and (ii) by all BW strata combined for STP206 low dose, STP206 high dose and control group. Incidence rate of suspected NEC (stage I), confirmed NEC (stage II and higher) will be further summarized by two subgroups: gestational age at birth is less than and equal to 28 weeks, and greater than 28 weeks.

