14.1.4.2.1	Maternal Concomitant Medications by Drug Class and Preferred Name by Birth Weight Stratification (2000-1501 g,1500–1000 g)\Safety Population
14.1.4.2.2	Maternal Concomitant Medications by Drug Class and Preferred Name by Birth Weight Stratification (999 - 750 g, 749 – 500 g)\Safety Population
14.1.4.2.3	Maternal Concomitant Medications by Drug Class and Preferred Name Across All Birth Weight Stratifications\Safety Population
14.1.4.3.1	Infant Prior Medications by Drug Class and Preferred Name by Birth Weight Stratification (2000 - 1501 g, 1500 – 1000 g)\Safety Population
14.1.4.3.2	Infant Prior Medications by Drug Class and Preferred Name by Birth Weight Stratification (999 - 750 g, 749 – 500 g)\Safety Population
14.1.4.3.3	Infant Prior Medications by Drug Class and Preferred Name Across All Birth Weight Stratifications\Safety Population
14.1.4.4.1	Infant Concomitant Medications by Drug Class and Preferred Name by Birth Weight Stratification (2000 - 1501 g, 1500 – 1000 g)\Safety Population
14.1.4.4.2	Infant Concomitant Medications by Drug Class and Preferred Name by Birth Weight Stratification (999 - 750 g, 749 – 500 g)\Safety Population
14.1.4.4.3	Infant Concomitant Medications by Drug Class and Preferred Name Across All Birth Weight Stratifications\Safety Population
14.2.2.1	Incidence Rate of NEC by Birth Weight Stratification (2000 - 1501 g, 1500 – 1000

	g)\Intent-to-treat Population
14.2.2.2	Incidence Rate of NEC by Birth Weight Stratification ((999 - 750 g, 749 – 500 g)\Intent-to-treat Population
14.2.2.3	Incidence Rate of NEC Across All Birth Weight Stratifications\Intent-to-treat Population
14.2.2.6	Incidence Rate of NEC by Birth Weight Stratification (2000 - 1501 g, 1500 – 1000 g) and Gestational Age Group(<= 28 Weeks, > 28 Weeks)\Intent-to-treat Population
14.2.2.7	Incidence Rate of NEC by Birth Weight Stratification ((999 - 750 g, 749 – 500 g) and Gestational Age Group(<= 28 Weeks, > 28 Weeks)\Intent-to-treat Population
14.2.2.8	Incidence Rate of NEC Across All Birth Weight Stratifications and Gestational Age Group(<= 28 Weeks, > 28 Weeks)\Intent-to-treat Population
14.2.3.1	Incidence Rate of Sepsis, Feeding Intolerance and Antibiotic Use by Birth Weight Stratification (2000 - 1501 g, 1500 – 1000 g)\Intent-to-treat Population
14.2.3.2	Incidence Rate of Sepsis, Feeding Intolerance and Antibiotic Use by Birth Weight Stratification (999 - 750 g, 749 – 500 g)\Intent-to-treat Population

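### Infection with an STP206 organism is a stopping event, but the SAP plans no by-arm summary of it, and the SAP's blood-culture wording is narrower than the protocol's sepsis work-up

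*SAP*

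**What the plan says.** **The harm the protocol singles out.** Protocol 5.5 lists infection, including bacteremia, among the possible adverse events. Protocol 7.1.1 makes this a stopping event: "Isolation of an STP206 organism from a normally sterile site (including bacteremia but excluding peritonitis in association with intestinal necrosis) in any subject". No time limit is attached. Under Protocol 10.3.5.1, if the local laboratory finds gram-positive bacilli in blood, "a sample of the isolate will be forwarded to the central laboratory for qPCR analysis to confirm" whether they are STP6 or STP11. Protocol 10.3.5.2 does the same for other normally sterile sites.

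**How the SAP analyses it.**
- SAP 8.6.2.1 lists "Incidence of sepsis/bacteremia" as a secondary efficacy endpoint, with no mention of organism.
- SAP 8.6 adds: "The analyses of efficacy variables will be performed for ITT population only".
- The matching outputs in SAP 11 are Tables 14.2.3.1 to 14.2.3.3, "Incidence Rate of Sepsis, Feeding Intolerance and Antibiotic Use by Birth Weight Stratification" and across all strata.
- For blood cultures, SAP 8.7.3 covers NICU admission and then "during the dosing period when sepsis is suspected. Data from blood cultures will be provided in a listing". For other sites, "Data from site cultures will be provided in a listing"; no period is stated for these.

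**The endpoint window.** Protocol 6.3.2 defines the secondary endpoint as "The incidence of clinical events (NEC, sepsis/bacteremia, feeding intolerance, death, morbidity/complications of prematurity) in STP206-treated subjects compared to control subjects from baseline through hospital discharge". SAP 8.6.5 also takes sepsis to hospital discharge.

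**The concern.** For a live bacterial product, a bloodstream infection can mean two opposite things. Infection with an ordinary pathogen is an event the product might prevent. Infection with STP6 or STP11 is an event the product causes. A sepsis percentage that does not distinguish organisms adds the two together, and it sits among the efficacy results, analysed by randomized arm. If the product lowered the first and raised the second, that figure could show no difference.

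The final report would then carry the product-specific harm only as individual lines in listings, with no numerator, denominator or confidence limit by arm. For a phase Ib study whose primary objective is safety, this is a number a reader would look for, including when it is zero.

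The culture wording adds a smaller problem. If a programmer followed SAP 8.7.3 literally, blood cultures taken after the last dose would not be part of the described data, although the sepsis outcome and the AE period both continue beyond that point.

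**Working it through.** The plan states no figure to reproduce: the sample size has no statistical basis (Protocol 13.1, SAP 4.5). The check is of planned outputs and windows, with arithmetic for scale.

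**1. Outputs in SAP 11 that could show the result.**
- Tables naming STP206 organisms: 14.3.6.4.1 to 14.3.6.4.3 only, and these are for fecal samples.
- Sepsis by arm: Tables 14.2.3.1 to 14.2.3.3, ITT, with no organism in the title.
- Cultures and organism: Listings 16.2.6.2.1 (sepsis cultures), 16.2.6.2.2 (gram bacilli result) and 16.2.7.5 (sterile-site infection). None has a matching table.
- SAP 6.4.2 includes a count of subjects with an STP206 organism identified and does not name the specimen. The related text in SAP 6.6 and 8.7.4 and the only matching tables are fecal, so this does not fill the gap.

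**2. The second by-arm route.** Protocol 10.3.5.1 makes any sepsis an SAE, and Protocol 12.2.3 does so for all confirmed bacteremia. SAP 8.7.2 tabulates SAEs by arm, SOC and preferred term in the safety population. Two things weaken this route.
- The tables have no STP206-organism category and no stated link to the qPCR result.
- Protocol 10.5.2.5 lists late-onset sepsis among complications of prematurity, and Protocol 10.3.5 and 12.3.1 say such complications are not recorded or classified as AEs. That contradicts 10.3.5.1 and 12.2.3.

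**3. Windows side by side.**

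| Item | Period stated |
|---|---|
| Blood cultures, SAP 8.7.3 | NICU admission; dosing period |
| Site cultures, SAP 8.7.3 | none stated |
| Sepsis work-up, Protocol 10.3.5.1 | no limit |
| Stopping event, Protocol 7.1.1 | no limit |
| Sepsis outcome, Protocol 6.3.2 and SAP 8.6.5 | to hospital discharge |
| AEs and SAEs, Protocol 12.1 | to 6 months after last dose |

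**4. Planned size.** Eight groups of 12 (Protocol 7.1) give 8 × 12 = 96. At 2:1 this is 64 STP206 (32 per dose) and 32 control, or 8 and 4 per group.

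**5. What a zero count would say.** The two-sided 95% exact upper limit with no events is 1 − 0.025^(1/n):
- n = 64: 5.6%
- n = 32: 10.9%
- n = 8: 36.9%
- n = 4: 60.2%

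The pooled figure is informative; the per-cell ones are not.

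**6. Illustration of masking (assumed counts, not from the documents).** Suppose the STP206 arms have 5 ordinary and 3 product-organism cases, and control has 4 ordinary cases. The sepsis row reads (5 + 3)/64 = 12.5% against 4/32 = 12.5%. The split row would read 3/64 = 4.7% (exact 95% CI 1.0% to 13.1%).

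**The case against.** **The event is visible anyway.** Each confirmed isolate halts enrollment and goes to the DSMC, whose review is unblinded once a stopping criterion is met (Protocol 7.1.1, 10.3.5.1, 10.3.5.2). Protocol 12.4.1 requires reporting of confirmed product infections even when they are not SAEs. Three such events passing unnoticed is not realistic. This stands as to trial conduct, and it is why the masking example is only an illustration. It does not supply a by-arm result in the final report.

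**Listings suit rare events.** Protocol 10.3.5.1 regards sepsis with the organism it names (redacted) as extremely rare and not anticipated, and one listing is specific to gram bacilli. This is a fair defence of listings for the case detail. A zero with its upper limit is still a summary that listings do not give.

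**The harm is not hidden in one percentage.** A reader might infer that the sepsis efficacy table is the only place where arms are compared. The SAE tables contradict that, and an investigator's diagnosis that names the organism could survive coding. Nor are all such infections pooled into sepsis: sterile-site infections other than sepsis are in no sepsis table. Both points stand and limit the claim.

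**The culture data do not stop at the end of dosing.** A reader might infer from SAP 8.7.3 that they do. The section says when blood cultures are collected; it sets no data cut-off. The listings carry none, SAP 8 takes summary tables to Month 6, and the protocol does not confine cultures to dosing. This stands: days outside the dosing period do not measure lost data.

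**The shells are separate.** SAP 11 says so and allows extra tables, so an organism row in Tables 14.2.3.x cannot be ruled out. Nothing in the SAP text calls for one.

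**Conclusion.** The point holds in a limited form. The SAP text and its output schedule contain no by-arm summary of infection confirmed as STP6 or STP11, although the protocol treats a sterile-site isolate as a stopping event and already requires the typing. The all-organism sepsis outcome cannot separate product harm from possible benefit. The SAE tables help, but they lack an organism category and depend on sepsis reporting rules that contradict each other.

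The culture wording in SAP 8.7.3 conflicts with the protocol work-up and with the SAP's own sepsis window. It should be corrected as wording, not read as evidence of discarded data.

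This is a worthwhile, inexpensive improvement and does not threaten the study. Its size rests on the planned 64 STP206 and 32 control infants: a zero count would carry a two-sided 95% upper limit of 5.6% pooled and 10.9% per dose. The documents give no expected rate of product-organism infection, so no likely number of events can be stated.

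**What to change.** 1. **Add one safety-population table by treatment received.** Columns: STP206 low dose, STP206 high dose, all STP206, control. Rows: infants with any culture-positive sterile-site infection, split into STP6 or STP11 confirmed by central qPCR and other organisms, with onset shown as during or after dosing. Give an exact 95% CI for the confirmed row in the pooled arms, all birth-weight strata combined. By stratum, give counts only.
2. **Show the same organism split** beneath the sepsis row of Tables 14.2.3.1 to 14.2.3.3.
3. **Reword SAP 8.7.3** so that all blood and site cultures obtained under Protocol 10.3.5.1 and 10.3.5.2 are reported, whether taken during or after dosing. The wording should describe what is reported and should not require new cultures.
4. **Reconcile** Protocol 10.3.5, 10.5.2.5 and 12.3.1 with 10.3.5.1 and 12.2.3 on whether sepsis is recorded as an AE or SAE, and state the outcome in SAP 8.7.2 so that the SAE tables can be interpreted.

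Cost: SAP wording, a protocol clarification, one new table and added rows in three others. The cultures and the qPCR typing are already required. The table will be sparse, and post-dosing culture entries must be kept in the analysis dataset. Isolates taken after discharge at another facility may not reach the central laboratory, so untyped gram-positive bacilli should be shown as such and not counted with other organisms.
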